6.4.4. Most Commonly Affected AD %BSA

Most commonly affected AD %BSA is collected at randomization, DB Days 169 and 365.

- Analysis Population: Evaluable-DB.

- Method: Descriptive summary for continuous endpoint.
- Reporting results: The number of participants, mean, standard deviation, median, minimum, maximum by DB treatment assignment for observed value and change from randomization to Days 169 and 365.

6.4.5. Duration of Flare-free periods

- Analysis Population: Evaluable-DB.
- Method: Descriptive summary for continuous endpoint. The average duration of flare-free periods (sum of durations/number of flare-frees) will be calculated for each participant, then summarize the average duration.
- Reporting results: The number of participants, mean, standard deviation, median, minimum, maximum.

6.4.6. Patient Reported Outcome Endpoints

PRO endpoints include:

- Pruritus and Itch Assessments, will be analyzed separately by age group:
 - Peak Pruritus NRS for participants ≥ 12 years of age;
 - PRIS Scale for participants 6- <12 years of age;
 - ORIS Scale for participants 3 months- <6 years of age.
- Night Time Itch Scale for participants ≥ 12 years of age.
- AD Skin Pain NRS for participants ≥ 12 years of age.
- PGIS/OGIS for all participants, will be analyzed separately by age group:
 - PGIS for participants ≥ 12 years of age;
 - OGIS for participants 3 months- <12 years of age.
- PGIC/OGIC for all participants, will be analyzed separately by age group:
 - PGIC for participants ≥ 12 years of age;
 - OGIC for participants 3 months- <12 years of age.
- MOS-Sleep Scale for participants ≥ 12 years of age.
- EQ-5D for all participants, will be analyzed separately by age group:
 - The EQ-5D-5L (5 levels) for participants ≥ 18 years of age;
 - The EQ-5D-Y (3 levels) for participants 8- <18 years of age;
 - The EQ-5D-Y Proxy (3 levels) for participants 2- <8 years of age.

- Work and Classroom Productivity for participants ≥ 12 years of age.
- HADS for participants ≥ 12 years of age.
- Dermatology quality of life assessments, will be analyzed separately by age group:
 - DLQI for participants ≥ 16 years of age;
 - CDLQI for participants 4- <16 years of age;
 - IDQoL for participants 3 months- <4 years of age.
- POEM: POEM for Proxy Completion (e.g., by parent), participants ages 3 months- <12 years of age, and POEM for Self Completion, participants ≥ 12 years of age.

All these PRO endpoints will be summarized as below:

- OL period:
 - Analysis Population: Evaluable-OL.
 - Method: Descriptive summary for continuous endpoint.
 - Reporting results: The number of participants, mean, standard deviation, median, minimum, maximum for observed value and change (except dermatology quality of life assessments, POEM and PGIC/OGIC) from OL baseline by time point.
- DB period, First flare-free period, and First flare period:
 - Analysis Population: Evaluable-DB.
 - Method: Descriptive summary for continuous endpoint.
 - Reporting results: The number of participants, mean, standard deviation, median, minimum, maximum for observed value and change (except PGIC/OGIC) from randomization in the DB period (Flare-free/Flare), the first flare-free period, and the first flare period. For the first flare period, the change is the change from the start of first flare period, summary is performed by the time point relative to the start of first flare period (ie, Weeks 0, 4, 8, 12 in the first flare period).

6.5. Subset Analyses

The primary endpoint (main analysis only) and key secondary endpoints number of flare-free days and number of flares will be analyzed by age group (3 months- <12 years, ≥ 12 years), ISGA score (clear, almost clear) at randomization, race (White, Black, Asian, Other), ethnicity (Hispanic, Non-Hispanic), and number of OL weeks (≤ 4 , >4) before randomization.

6.6. Baseline and Other Summaries and Analyses

6.6.1. Baseline Summaries

Demographics and baseline characteristics listed in [Section 3.5](#) will be summarized for SAF-OL, and SAF-DB by QD treatment group according to Pfizer standards.

For Evaluable-DB, the efficacy and PRO data at randomization will be summarized by QD treatment group according to Pfizer standards. For daily assessed endpoints (eg, pruritus, itch, pain, etc.), weekly average before randomization will be used.

6.6.2. Study Conduct and Participant Disposition

Participants evaluation, disposition, discontinuation will be summarized, separately for OL period and DB period according to Pfizer standards.

6.6.3. Study Intervention Compliance

A participant will be considered compliant with the dosing regimen if they receive 80%-120% of the expected number of doses in accordance with the protocol. The number and percentage of participants who are compliant with the dosing regimen, number of dosing days and number of applications, and amount of intervention used will be summarized by OL period, QD period, and flare treatment period.

6.6.4. Concomitant Medications and Nondrug Treatments

Prior drug and non-drug treatment, concomitant drug and non-drug treatment will be summarized according to Pfizer standards.

6.7. Safety Summaries and Analyses

Safety analyses will be based on the SAF-OL, SAF-DB, according to the period and endpoint.

All clinical AEs, SAEs, TEAEs, withdrawal due to AEs, vital signs and safety laboratory data will be reviewed on an ongoing basis during the study to evaluate the safety of participants.

Safety data will be presented in tabular and/or graphical format and summarized descriptively, where appropriate. All safety endpoints will be listed and summarized in accordance with Pfizer Standards. Categorical outcomes (eg, AEs) will be summarized by participant counts and percentage. Continuous outcome will be summarized using N, mean, median, standard deviation, etc. Participant listings will be produced for these safety endpoints accordingly.

Separate listings and/or summaries may be produced for participants who are impacted by COVID-19, have protocol deviations, discontinue from study or study treatment due to the COVID-19 pandemic.

6.7.1. Adverse Events

The safety data will be summarized separately by period: OL period for SAF-OL, DB QD period for SAF-DB, and flare treatment period for SAF-DB in accordance with Pfizer Data Standards. All safety data will be summarized descriptively through appropriate data tabulations, descriptive statistics, categorical summaries, and graphical presentations. The safety data will be summarized for overall events and treatment area events. Safety endpoints for the study include:

- Incidence of TEAEs.
- Incidence of SAEs and AEs leading to discontinuation.

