3. OBJECTIVES, ESTIMANDS AND ENDPOINTS

Objectives	Endpoints
Primary	

Efficacy: To evaluate the long-term efficacy of crisaborole ointment, 2%, QD for maintenance therapy and flare reduction in pediatric and adult participants ≥ 3 months of age with mild-to-moderate AD who responded to crisaborole ointment, 2%, BID treatment.	
Flare-free maintenance until onset of first flare during the 52-week double-blind period

Safety: To evaluate the safety and local tolerability of crisaborole ointment, 2%, QD for maintenance therapy and flare reduction in pediatric and adult participants ≥ 3 months of age with mild-to-moderate AD	
Incidence of treatment emergent adverse events
Secondary	

To evaluate other long-term efficacy parameters for maintenance therapy and flare reduction of crisaborole ointment, 2%, QD in pediatric and adult participants ≥ 3 months of age	Key secondary endpoints during the 52-week double-blind period: 
Number of flare-free daysNumber of flares

with mild-to-moderate AD who responded to crisaborole ointment, 2%, BID treatment
	
 • Pruritus response maintenance until onset of first flare 
Other secondary endpoints during the 52-week double-blind period:
 
 • $\geq 50\%$ reduction in Eczema Area and Severity Index (EASI)50 response maintenance • Maintenance of Dermatology Quality of Life Assessments • Maintenance of Patient Oriented Eczema Measure (POEM) 
The following will be assessed during flare treatment period:
 
 • Severity of flare on Investigator’s Static Global Assessment (ISGA) and EASI • Duration of flare episode

Additional Secondary
	

 • To evaluate the long-term efficacy of crisaborole ointment, 2%, QD for maintenance therapy and flare reduction in participants ≥ 3 months of age with mild-to-moderate AD 	
The following will be assessed as change from baseline of each respective treatment period (run-in, double-blind, and flare treatment):
 
 • EASI scores • ISGA scores • Treatable AD %BSA • Most commonly affected AD %BSA

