9.3. Populations for Analyses

For purposes of analysis, the following populations are defined:

Population	Description
Enrolled	All participants who sign the ICF.
Evaluable – Open Label (Evaluable-OL)	All participants receiving at least 1 dose of study intervention in the open-label run-in period
Evaluable – Double-Blind (Evaluable-DB)	All randomized participants receiving at least 1 dose of study intervention in the double-blind maintenance period. Participants will be analyzed according to the intervention they are randomized to.
Safety – Double-Blind (Safety-DB)	All participants randomly assigned to study intervention and who take at least 1 dose of study intervention in the double-blind maintenance period. Participants will be analyzed according to the intervention they actually received.
Safety – Double-Blind Maintenance Period (excluding data from flare treatment period) (Safety-QD)	All participants randomly assigned to study intervention and who take at least 1 dose of study intervention in the double-blind maintenance period (excluding data from the flare treatment period). Participants will be analyzed according to the intervention they actually received. Safety data from flare treatment periods will be summarized separately.
Safety – flare treatment period (Safety-flare)	All participants who receive at least 1 dose of study intervention in the flare treatment period during the double-blind maintenance period. Participants will be analyzed according to the intervention they received in QD period.

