9.4.2. Safety Analyses

All safety analyses will be performed on the Safety Population.

Endpoint	Statistical Analysis Methods
Primary	
AEs, SAEs, local tolerability, discontinuations, and clinically significant changes in vital signs will be descriptively summarized and will be presented in tabular and/or graphical format by open-label run-in period, flare treatment period in the maintenance period, and QD period. No imputation will be made for missing safety data.

CCI

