3.6.1. Adverse Events

An AE is considered treatment-emergent adverse event (TEAE) to a given treatment (for a participant who received at least one dose) if the event start date is on or after the treatment period start date and before end of study.

Safety endpoints will be assessed by the spontaneous reporting of:

- Incidence of TEAEs;
- Incidence of serious adverse events (SAEs);
- Incidence of AEs leading to discontinuation.

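### Adverse event summaries are specified only by period: add a supplementary whole double-blind summary by arm, with exposure-adjusted rates

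*SAP*

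**What the plan says.** The primary safety endpoint in Protocol 3 is "Incidence of treatment emergent adverse events", with no period named.

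- **Protocol 9.3** has three double-blind safety rows. Safety-DB is "All participants randomly assigned to study intervention and who take at least 1 dose of study intervention in the double-blind maintenance period", analysed by intervention actually received. Safety-QD repeats those words but excludes flare-period data, adding "Safety data from flare treatment periods will be summarized separately". Safety-flare covers participants dosed during flare treatment.
- **Protocol 9.4.2** presents safety "by open-label run-in period, flare treatment period in the maintenance period, and QD period". It gives Safety-DB no whole-period table.
- **SAP 6.7** says "Safety analyses will be based on the SAF-OL, SAF-DB, according to the period and endpoint", and reports categorical outcomes such as adverse events as numbers and percentages of participants.
- **SAP 6.7.1** says "The safety data will be summarized separately by period: OL period for SAF-OL, DB QD period for SAF-DB, and flare treatment period for SAF-DB". It adds "The safety data will be summarized for overall events and treatment area events", where overall is set against treatment-area events and does not mean all periods combined.
- **SAP 3.6.1** counts an event as treatment-emergent "if the event start date is on or after the treatment period start date and before end of study". Nothing cuts that window at the start of flare treatment.
- **SAP 4** keeps SAF-DB (as received), adds a whole-study SAF set to which no table is assigned, and has no Safety-flare row.
- **SAP Appendix 3** gives generic endpoint shells, all split by flare-free and flare period.

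**The concern.** Flare is the efficacy outcome, and each one moves the participant from blinded QD treatment to 4 to 12 weeks of open-label BID crisaborole (Protocol 4.1). If crisaborole works, vehicle participants spend less time on QD. A crude percentage over QD time then compares arms with unequal time at risk. Only participants who flared can contribute an event to the flare-period summary. One participant can have an event in each, so the two incidences do not add up to a 52-week figure.

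Protocol 4.2 describes an evaluation of 52-week safety, yet no specified summary follows the double-blind groups through that period. The attribution of flare-onset events is also unsettled: under SAP 3.6.1, read literally, an event starting in a flare course is still emergent to the QD treatment, while the by-period split implies that it belongs to the flare summary.

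**Working it through.** **1. The plan's own figure.** Protocol 9.2: 162 first flares, hazard ratio 0.556, two-sided 0.05, 1:1. Power = Φ(√(162/4) × |ln 0.556| − 1.960) = Φ(3.736 − 1.960) = 0.962. The stated 96% reproduces. The point does not rest on it; the design values only serve to size flare time.

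**2. Share affected.** 162/250 = 64.8% of randomised participants are planned to have a first flare. One flare treatment period takes 4/52 = 7.7% to 12/52 = 23.1% of the double-blind year.

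**3. First flares by arm.** Assume exponential flare times, 125 per arm and 52 weeks without dropout. Solve 125(1 − e^(−λ)) + 125(1 − e^(−0.556λ)) = 162. This gives λ = 1.403 per 52 weeks. First flares are then 94.3/125 = 75.4% on vehicle and 67.7/125 = 54.2% on crisaborole.

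**4. Simulated year.** Flares recur at these rates. Courses last 4 weeks, at most three in a row, and non-resolvers leave (Protocol 4.1). Not in the documents, so assumed: a resolution chance per course of 30%, 60% or 95%; no frailty; the same adverse event hazard of 1% per week in both arms, on QD and in flare courses. Expected incidence is the mean of 1 − exp(−0.01 × weeks at risk). Each cell is crisaborole v vehicle.

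| Resolution per course | Share of time in flare courses | QD-period incidence | Gap | Whole-period incidence | Gap |
|---|---|---|---|---|---|
| 30% | 10.8% v 17.8% | 34.4% v 30.6% | 3.8 | 38.1% v 36.4% | 1.7 |
| 60% | 7.9% v 13.6% | 37.5% v 35.2% | 2.3 | 40.1% v 39.7% | 0.4 |
| 95% | 5.7% v 9.8% | 38.7% v 37.4% | 1.3 | 40.5% v 40.5% | 0.0 |

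The true hazards are equal, so every gap is an artefact of unequal time. The gap left in the whole-period column comes from non-resolvers leaving, more of them on vehicle. A rate per unit of time at risk would be 1% per week in both arms.

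**5. Second version.** With fixed course lengths, everyone resolving, and a hazard of 0.5 per 52 weeks, the true incidence is 1 − e^(−0.5) = 39.3% in each arm. The QD-period table reads 37.6% v 36.4% with 4-week courses (gap 1.2) and 34.8% v 31.9% with 12-week courses (gap 2.9).

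**6. Why the tables do not add.** Take a hypothetical arm with 30/125 in the QD table and 12/125 in the flare table. If all 12 are among the 30, the double-blind incidence is 30/125 = 24.0%. If none are, it is 42/125 = 33.6%. The two tables fit anything between.

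**The case against.** The strongest reply is that pooling has its own bias. During flares the vehicle arm receives active BID drug. Protocol 2.3 reports treatment-related application site pain of 4.4% on crisaborole BID and 1.2% on vehicle, a ratio of 3.7. Suppose that ratio applied both to QD crisaborole and during flare courses. This is an assumption: the pain was mostly early and transient, and these participants had already used BID. With 9.8% to 17.8% of vehicle time in flare courses, the vehicle rate rises by a factor of 1 + 0.098 × 2.67 = 1.26 to 1 + 0.178 × 2.67 = 1.47. The crisaborole to vehicle ratio then falls from 3.7 to between 2.9 and 2.5. Pooling can therefore hide a real local-tolerability difference, whereas under equal hazards the QD table errs against crisaborole. This stands, and it is why the pooled table should be supplementary.

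Other replies also stand:

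- The safety objective is worded around crisaborole QD, and the QD-period summary on SAF-DB gives one incidence per arm over all dosed randomised participants. A reader might infer that the primary safety endpoint is never given as one incidence per arm; that is true only of the whole double-blind period.
- A reader might infer that the SAP dropped a protocol table. It did not: Protocol 9.4.2 has the same split, and the SAP keeps SAF-DB.
- SAF-DB is analysed as received, so the gap concerns arms as received.
- The SAP defers to sponsor standards that are not shown. The documents support that the table is not specified, not that it will not be produced.
- A gap of 1 to 4 points is small beside a standard error of √(2 × 0.36 × 0.64/125) = 6.1 points, and safety is descriptive with no decision rule.

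None of these replies supplies a whole-period summary, an exposure adjustment or an attribution rule.

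**Conclusion.** The point holds as a gap in specification. Both documents plan adverse event summaries by period only; no summary counts each SAF-DB participant once over the double-blind period; and SAP 3.6.1 does not agree with the split. The QD-period percentages carry an exposure imbalance of about 1 to 4 points against crisaborole. That size rests on the design hazard ratio, exponential flares, no dropout, and an assumed equal hazard of about 1% per week on QD and in flare courses. A whole-period count reduces it to 0 to 1.7 points.

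A reader might go further and infer that every between-arm safety comparison is made on people selected by the efficacy outcome. The text does not support that: the QD summary includes all of SAF-DB and differs only in time at risk, and SAP 6.7.1 also assigns the flare summary to SAF-DB. Nor is it settled that a flare-onset event leaves the QD table, given the window in SAP 3.6.1. This is a cheap improvement and does not threaten the trial's conclusions.

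**What to change.** In SAP 6.7.1:

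- Add a supplementary SAF-DB table set by double-blind arm as received, from first double-blind dose to the end of double-blind follow-up, flare periods included. Cover TEAEs, SAEs, adverse events leading to discontinuation and treatment-area events, each participant counted once.
- Give exposure-adjusted rates for this set and for the QD-period table.
- Keep the by-period tables, and do not name the pooled set as the primary presentation.
- State to which period a flare-onset event is attributed, and bring SAP 3.6.1 into line.
- Footnote that both arms received open-label crisaborole BID during flares.

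The cost is one table set, person-time denominators and a few sentences. No new data are needed, and sample size and power do not change. The downside is that the pooled set mixes QD or vehicle exposure with BID exposure and can dilute local-tolerability differences; the retained QD-period table shows those.

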6.7.2. Laboratory Data

Laboratory data will be listed in accordance with the Pfizer reporting standards.

6.7.3. Vital Signs

Vital signs data will be listed.

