		
flare-free days and number of flares as primary analysis
 
 • Treat duration of per flare period and duration of per QD period as continuous endpoints, not as time-to-event • Additional summary for overall DB period for efficacy/PRO endpoints • LOCF data will be used for OL period efficacy summary. • Added additional age subgroup analyses for primary and key secondary efficacy endpoints, evaluation and disposition groups, demographic and baseline characteristics, AE data 	
discontinuation into consideration
 
 • May have too many censor data • Provide efficacy/PRO summary for overall DB period • Based on study design (ie, responders at any time during OL period will be randomized into the DB period) • Per Article 46 requirement
4 20Jan2022	Amendment 1 19May2020	
 • Summary of vital signs (including height and weight) and physical exam was removed • Added safety population for OL 	
 • Team decision • For convenience and consistency among safety tables

		
period and overall study.
 
 Removed subgroup analysis by age groups 3 - <24 months, 2 - <12 years, 12 - <18 years, and ≥ 18 years Removed subgroup analysis for key secondary endpoint maintenance of pruritus response. Removed sensitivity analysis for number of flare-free days and number of flares (annualized data) Prohibited treatment use was removed from intercurrent events 	
 Article 46 no longer apply There are already 5 subgroups for maintenance of pruritus response. Sample size will be too small and may not get robust results by further subgroup analysis. Observed data are more appropriate. Difficult to identify prohibited medication specifically used for AD.
--	--	---	--

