3.6. Safety Endpoints

Safety will be assessed by vital signs, physical examinations, clinical laboratory tests and the spontaneous reporting of adverse events (AEs), in all participants who received at least one dose of study intervention. Unscheduled safety assessments may be performed at any time during the study to assess any perceived safety concerns. Investigators and Pfizer Clinicians will review individual participant data throughout the conduct of the study to ensure participants' well-being. Appendix 5 of the protocol provides liver safety (Suggested Actions and Follow-up Assessments) in details.

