6.7.4. Physical Examination

Physical examination data will be listed.

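### Protocol 9.4.2 calls for a descriptive summary of clinically significant vital-sign changes by study period, but SAP 6.7.3 provides only a listing, and the sole reason recorded for the change is a team decision.

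*SAP*

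**What the plan says.** Protocol 9.4.2, in the row labelled as primary, states: "AEs, SAEs, local tolerability, discontinuations, and clinically significant changes in vital signs will be descriptively summarized". It asks for tables and/or graphs, split into the open-label run-in, the flare treatment periods and the QD periods. Protocol 8.2.3 and SAP 3.6.3 define vital signs as temperature and pulse rate.

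The SAP handles the same data differently in different places:

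- SAP 3.6 keeps them as a safety assessment: "Safety will be assessed by vital signs, physical examinations, clinical laboratory tests and the spontaneous reporting of adverse events".
- SAP 6.7 gives a general rule: "All safety endpoints will be listed and summarized in accordance with Pfizer Standards".
- SAP 6.7.3 gives the specific rule: "Vital signs data will be listed". SAP 6.7.4 does the same for examinations: "Physical examination data will be listed".
- SAP 1, in the version 4 entry, records "Summary of vital signs (including height and weight) and physical exam was removed", with "Team decision" in the rationale column. Version 4 is still tied to protocol Amendment 1, so Protocol 9.4.2 stands as written.

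**The concern.** The two current documents give different instructions for the same safety data, and no scientific reason is recorded for the difference. The version history is not the source of the conflict. It only shows that the listing-only wording in SAP 6.7.3 was deliberate and not a slip.

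A listing shows individual values. It cannot show whether pulse or temperature moved differently on crisaborole and on vehicle. Post-baseline laboratory tests are done only if clinically indicated, so temperature and pulse are among the few numerical systemic measures taken on a schedule in both arms over 52 weeks, in participants from 3 months of age. Without a summary, the report would have no group-level description of them after baseline.

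**Working it through.** The plan states no figure on this point, so the check compares the texts and then counts the data affected.

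**Comparison of texts**

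1. Requirement: Protocol 9.4.2 asks for a summary of clinically significant vital-sign changes in each of three period types.
2. Delivery: SAP 6.7.3 gives a listing, with no table, no period split and no arm split.
3. Could SAP 6.7 supply the summary? Its general sentence promises one, and it adds that continuous safety outcomes get the usual descriptive statistics. But laboratory data (6.7.2), vital signs (6.7.3) and physical examinations (6.7.4) are each listed only, and 6.7.1 covers adverse event incidence. No continuous safety outcome with a specified summary is left for that sentence to govern. A programmer would follow the specific sections, which agree with the version 4 entry.
4. Is there a post-baseline summary elsewhere? SAP 3.5 and 6.6.1 summarise height, weight and BMI at baseline only, and do not include temperature or pulse. No other section does.

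**Data affected**

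- Protocol Table 1 schedules vital signs at every in-clinic visit. In the maintenance period these are Weeks 0, 4, 8, 12, 16, 24, 32, 40, 48 and 52, which is 10 visits. Weeks 20, 28, 36 and 44 are by phone.
- Leaving out the randomisation visit: 10 − 1 = 9 post-randomisation in-clinic visits.
- With about 250 randomised participants (Protocol 9.2): 9 × 250 = 2,250 sets of temperature and pulse.

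This is an upper limit for scheduled visits. Dropout lowers it, and so do pandemic phone contacts, whose list of assessments in Protocol Appendix 9 has no vital signs. It also includes visits during flare treatment, when both arms receive open-label BID crisaborole. Only the QD-period sets contrast crisaborole with vehicle. The documents do not allow that subset to be counted in advance.

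**The case against.** The strongest reply is that little is lost. Protocol 10.3.1 makes an abnormal vital sign an adverse event when the investigator judges it clinically significant, and SAP 6.7.1 tabulates treatment-emergent events by period. Targeted physical examinations are scheduled at every in-clinic visit, vital signs are reviewed during the study, and an external committee monitors safety. Protocol 2.2.1.2 says systemic absorption has no clinically relevant pharmacological effect, and 2.2.1.3 reports no important systemic signal down to 3 months of age.

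Much of this stands, and it rules out several stronger readings that a reader might infer:

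- *That the change breaches the protocol because no amendment was made.* Protocol 9.4 lets the SAP modify the plan. It requires an amendment only for major changes to primary or key secondary endpoints or their analyses. The primary safety endpoint is the incidence of treatment-emergent adverse events, not vital signs.
- *That Protocol 9.4.2 also requires height and weight summaries.* It names vital signs only. Height and weight fall under physical examinations in Protocol 8.2.2, and their randomisation values are still summarised by QD group.
- *That safety would rest on adverse events alone, or that these are the only objective scheduled data.* Examinations are also scheduled, although they too are only listed.
- *That the protocol demands a between-arm test.* It asks for a descriptive summary by period. The arm split follows from safety populations defined by intervention received.

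The reply does not remove the point. Adverse event capture depends on case-by-case judgement and cannot reveal a shift in group level. Protocol 9.4.2 names adverse events and vital-sign changes as separate items, so the first was not meant to stand in for the second.

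**Conclusion.** The point holds for temperature and pulse. A descriptive summary specified in Protocol 9.4.2 is missing from the SAP without a stated scientific reason, and SAP 6.7 contradicts SAP 6.7.3. The consequence is that no post-baseline summary by arm is planned for at most about 2,250 scheduled sets of measurements, assuming 250 randomised participants with full attendance and counting flare-period visits. That number measures unused data, not harm: nothing in the documents suggests that a difference between arms exists. No efficacy result, error rate or primary safety endpoint is affected. The change is worth making because it restores a planned part of the safety assessment at very low cost.

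**What to change.** In SAP 6.7.3, restore a descriptive summary of temperature and pulse giving the value, the change from randomisation, and the number of participants with a clinically significant change:

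- for SAF-DB, by double-blind QD arm (under that population's rule, the intervention actually received), separately for QD periods and flare periods;
- for SAF-OL in the run-in, with change taken from the open-label baseline.

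State which criterion defines a clinically significant change, since neither document gives limits for temperature or pulse. Align SAP 6.7 with the restored text and keep the listings.

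An optional addition, which Protocol 9.4.2 does not require, is a by-arm summary of height and weight change from randomisation to Days 169 and 365 in paediatric participants.

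The cost is a few more standard tables from data already collected, plus some descriptive noise. No new visits or procedures are needed.
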